7.3.1.2. Summary Measure

7.3.1.2.1. Progression-Free Survival

PFS is defined as the interval of time between the date of first dose and the earlier of the date of first disease progression and the date of death due to any cause. Disease progression will be based on the assessments by the Investigator.

If there is no adequate baseline assessment, the subjects will be censored at their date of first dose. Subjects without any adequate post-baseline tumor assessments will be censored at the date of first dose.

Subjects who progressed or died after an extended period without adequate assessment will be censored at their date of last adequate assessment prior to progression or death even if subsequent information is available regarding progression or death. An adequate assessment is defined as an assessment where the Investigator determined response is sCR, CR, VGPR, PR, MR or SD. The date of response at that assessment will be used for censoring. As the assessment schedule may change through the course of the protocol, specific rules for identifying extended loss to follow-up or extended time without an adequate assessment are provided in Section 16.5.4.

For subjects who receive subsequent anti-cancer therapy the following rules will apply:

- If the start date of the anti-cancer therapy is partial (i.e. either missing the day but has the month and year available or missing both day and month), the imputation rules described in Section 16.7.2.1 will be applied. No imputation will be made for completely missing dates.
- If anti-cancer therapy is started without documented disease progression or death OR is started prior to documented disease progression or death, then PFS will be censored at the date of the last adequate assessment that is no later than the date of initiation of anti-cancer therapy (i.e. if an assessment occurs on the same day as the start of new anti-cancer therapy the assessment will be used - as it will be assumed the assessment occurred prior to the administration of new anti-cancer therapy). The date of response at the last adequate assessment will be used as the censoring value.
- If a subject has only a baseline visit or does not have an adequate assessment that is no later than the date of initiation of anti-cancer therapy, PFS will be censored at the date of first dose.

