33. Optional follow-up telephone interview to explore visual symptoms and changes in symptoms and related impacts following treatment discontinuation be performed at least 6 months following the End of Study Treatment visit. This interview would only be for those subjects who experienced corneal symptoms during treatment and consent to participate.
34. End of treatment visit should be performed within 30 days (+7 days) after the last dose or prior to the start of new anti-cancer treatment, whichever is earlier. In cases where more than 30 days (+7 days) have elapsed from the date of the subject's last dose due to dosing delays and a subsequent decision to take the subject off treatment, the end of study treatment visit should be scheduled as soon as possible to allow the final assessments to be performed at the earliest date.

35. Participants with corneal signs or symptoms at the end of study treatment visit should be monitored by ophthalmic exam once a month after the last study dose until deemed clinically stable by an eye care professional complete resolution or for 12 months (whichever comes first). Corneal exams to include BCVA and slit lamp examination (with special focus on cornea). Participants who have completed treatment or the 3 month follow up visit (end of study) will be re-consented for additional ophthalmology follow up.

Abbreviations:

ADA = Antibody Drug Antibody; ALP = alkaline phosphatase; BCVA = best corrected visual acuity; BNP = B-type natriuretic peptide; C1D1 = Cycle 1 Day 1, etc.; cfDNA = Circulating free DNA; CK = creatinine kinase; CRP = C-reactive protein; EM = extramedullary; EOI = End of Infusion; FLC = free light chain; PD = Pharmacodynamics; PK = Pharmacokinetics; QID = 4 times a day; SOI = start of infusion; SPEP = serum protein electrophoresis; UPEP = urine protein electrophoresis

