16.5.5. Date Associated with Response

Investigator assessment of disease is entered in the eCRF on the VISIT form. The date of the VISIT is captured but the date of the response assessment is not captured separately. The date associated with response will be the visit date for the VISIT on which the investigator assessed disease. A disease assessment may occur at an unscheduled visit. The date of the unscheduled visit would be assigned to any response assessed on that date. In the following section, unless otherwise specified, the disease assessment denotes post-baseline assessment.

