Concomitant Medications	
 • Partial dates for any concomitant medications recorded in the CRF will be imputed using the following convention: 
 ○ If the partial date is a start date, a '01' will be used for the day and 'Jan' will be used for the month ○ If the partial date is a stop date, a '28/29/30/31' will be used for the day (dependent on the month and year) and 'Dec' will be used for the month. • The recorded partial date will be displayed in listings.
Anti-Cancer Therapy (Where applicable), Radiotherapy and Surgical Procedures for Time-to-Event Endpoint and Response	
 • Start dates for follow-up anti-cancer therapy, radiotherapy (where applicable), and surgical procedures (where applicable) will be temporarily imputed in order to define event and censoring rules for progression-free survival, response rate, time to progression, duration of response or time to response (i.e. start date for new anti-cancer therapy). The imputed dates will not be stored on the anti-cancer therapy, radiotherapy, or surgical procedure datasets. • If missing start day, month, and year, then no imputation for completely missing dates • If missing start day and month, then no imputation should be done • If missing start day, then do the following: 
 • If partial date falls in the same month as the last dose of study treatment, then assign to earlier of (date of last dose of study treatment+1, last day of month). • If partial date falls in the same month as the subject’s last assessment and the subject’s last assessment is PD, then assign to earlier of (date of PD+1, last day of month). • If both rules above apply, then assign to latest of the 2 dates • Otherwise, impute missing day to the first of the month. • If missing end date, then no imputation should be done.

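### The missing-day rule for new anti-cancer therapy checks only whether the last assessment is PD, so a PD followed by a later record can be imputed past and its PFS, TTP or DOR event censored

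*SAP*

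**What the plan says.** SAP section 16.7.2.1 states that start dates of follow-up anti-cancer therapy "will be temporarily imputed in order to define event and censoring rules for progression-free survival, response rate, time to progression, duration of response" and time to response. If only the day is missing, four bullets apply in turn:

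- Rule 1: "If partial date falls in the same month as the last dose of study treatment, then assign to earlier of" the day after the last dose and the month's last day.
- Rule 2: if the subject's last assessment is in that month and the "last assessment is PD, then assign to earlier of (date of PD+1, last day of month").
- Both: "If both rules above apply, then assign to latest of the 2 dates".
- Default: "Otherwise, impute missing day to the first of the month".

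The imputed date then drives the endpoints. Under section 7.3.1.2.1, if new therapy "is started prior to documented disease progression or death, then PFS will be censored at the date of the last adequate assessment" on or before the therapy start. Table 6 censors TTP in the same way, and section 7.3.1.2.3 makes DOR follow TTP. Section 7.2.1.1.1 closes the ORR window at the earlier of progression and new therapy.

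**The concern.** Rule 2 and the later-of-two clause have an evident purpose: an imputed therapy date should not jump ahead of a progression already on record. Rule 2 tests the wrong thing for that purpose. A PD in the therapy month that is followed by any further assessment record fails the test, even if that record carries no information. The date then falls back to the day after the last dose or to the first of the month, either of which can precede the PD.

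A documented progression then becomes a censoring at the preceding adequate assessment. Censoring a subject just before a known event is informative and pushes the Kaplan-Meier curves for PFS, TTP and DOR upward.

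A second consequence concerns ORR. No bullet looks at response assessments, so a confirming response seen after the last dose, in the month new therapy starts, can fall outside the response window.

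**Working it through.** The SAP states no figure on this point to reproduce. The check applies the section 16.7.2.1 bullets and the censoring rules to constructed dates.

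**Inputs.** The four bullets above. PFS censoring from section 7.3.1.2.1; Table 5 footnote 3 counts a PD on the same day as new therapy as an event, so the month-end cap does no harm. The 49-day gap rule of section 16.5.4 is not triggered, because the gaps below are 21 days. NE is in the response hierarchy of section 7.2.1.1.2, and section 16.7.2 does not treat a not-evaluable answer as missing. Section 16.5.5 says "Investigator assessment of disease is entered in the eCRF on the VISIT form" and allows assessments at unscheduled visits.

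**Progression.** Therapy is recorded only as March; the true start is after the PD.

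| Last dose | Assessments | Rule 1 | Rule 2 | Imputed start | PFS result |
|---|---|---|---|---|---|
| 15 Feb | SD 15 Feb, PD 8 Mar | no | 9 Mar | 9 Mar | event 8 Mar |
| 15 Feb | same, then NE 15 Mar, NE 5 Apr or PD 5 Apr | no | no | 1 Mar | censored 15 Feb |
| 1 Mar | SD 1 Mar, PD 22 Mar | 2 Mar | 23 Mar | 23 Mar | event 22 Mar |
| 1 Mar | same, then NE 5 Apr | 2 Mar | no | 2 Mar | censored 1 Mar |
| 8 Mar | PD 8 Mar, then NE 5 Apr | 9 Mar | no | 9 Mar | event 8 Mar |

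Rows 1 and 3 work as intended. In rows 2 and 4 the later record alone removes the event. In row 5 rule 1 protects the PD although it is not the last assessment. A PD on day 1 of the month, or in an earlier month, is also safe.

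**How often the rule fails once its conditions are met.** Assume a PD on a random day of a 365-day year, last dose 21 days earlier, a later NE, and therapy starting later in the PD month. The 12 month-end days leave no later day in the month: 365 − 12 = 353. Only a PD on day 1 escapes: 12 days. Share censored: (353 − 12)/353 = 341/353 = 96.6%. This says nothing about how often those conditions occur.

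**Response.** Therapy is again recorded as March.

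- PR 15 Feb with the last dose, confirming PR 8 Mar: the default gives 1 Mar. One assessment is left, so the confirmed response is NE (section 7.2.1.1.2), or SD if an SD came earlier.
- SD 8 Feb, PR 1 Mar with the last dose, confirming PR 22 Mar without a dose: rule 1 gives 2 Mar, and the confirmed response is SD.

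Either way the subject is a non-responder kept in the denominator (section 16.7.2). With up to 40 Part 2 MM subjects (section 2.3), one subject is 1/40 = 2.5 points. For illustration, 24/40 = 60.0% has an exact 95% CI of 43.3 to 75.1%; 23/40 = 57.5% has 40.9 to 73.0%.

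**The case against.** Much of the case for leaving the rule alone is sound.

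- **A record after PD is needed.** The Part 2 MM schedule (section 16.2.3.1) has no SPEP, UPEP or free light chain test at the end-of-treatment visit; plasmacytoma imaging is the only disease test there. A reader might infer that an NE is routinely recorded at that visit. The absence of marker tests suggests rather that PD will usually be the last assessment. Unscheduled assessments and imaging make a later record possible, not usual.
- **Last assessment might mean the last one considered.** Section 7.2.1.1.2 limits response derivations to assessments up to progression. Read that way, rule 2 would work. But section 16.7.2.1 does not say so, and a programmer following its words would not apply that limit.
- **The visit order is not guaranteed.** Footnote 34 asks for the end-of-treatment visit "prior to the start of new anti-cancer treatment, whichever is earlier", which might be read as proof that on-study assessments precede new therapy. The same footnote lets the visit come late after dosing delays, so it supports the expected order without establishing it.
- **The response default is partly a choice.** If therapy really began on 1 or 2 March, excluding an 8 March PR is what section 7.2.1.1.1 requires. First of the month is conservative for ORR. A responder with two qualifying assessments before that month is unaffected.

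What remains is the progression branch: where the later record exists, the literal rule gives a result contrary to its own purpose, and nothing else in the SAP prevents it.

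**Conclusion.** The defect holds in a limited form. It needs a start date with only the day missing, a PD in that same month after day 1 and after any same-month last dose, and a later NE or a repeat PD in a later month. Under those conditions the imputed start can precede the PD and a PFS, TTP or DOR event becomes a censoring.

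Two stronger readings are not supported. A reader might infer that PD is protected only when it is the last assessment; rule 1, a day-1 PD and an earlier-month PD show otherwise. A reader might also infer a definite lengthening of median PFS. The direction is upward, but the size depends on the number of partial dates and of records after PD, neither of which the SAP gives, so no figure can be attached and the effect may be nil.

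PFS, TTP and DOR are exploratory (section 2.2) and no hypothesis testing is planned for the MM cohort (section 2.4). The ORR consequence, 2.5 points per affected subject at N=40, touches a secondary endpoint but rests on an unknown true order. It calls for a sensitivity analysis rather than a correction.

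**What to change.** In section 16.7.2.1, reword the second bullet along these lines: *if a PD is documented in the month of the partial date, whether or not it is the last assessment, use the day after the first PD in that month, or the month's last day if that is sooner.* Keep the later-of-two clause with rule 1. Row 2 of the table then gives 9 March and row 4 gives the later of 2 and 23 March, so both events are kept.

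For ORR, keep the conservative default and add a sensitivity analysis that sets the start to the day after the latest on-study disease assessment in that month, capped at month end. Apply it under both rule 1 and the default: changing the default alone would miss the case of a last dose in the therapy month. Report the number of subjects with a day-missing therapy start, so that the reach of both points is visible.

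The cost is a line or two of text, a small programming change and one extra ORR summary. The downside is that an assessment made after an undocumented early therapy start could occasionally be kept.

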16.8. Appendix 8: Values of Potential Clinical Importance

16.8.1. Laboratory Parameters

Reference ranges for all laboratory parameters collected throughout the study are provided by the laboratory. A laboratory value that is outside the reference range is considered either high abnormal (value above the upper limit of the reference range) or low abnormal (value below the lower limit of the reference range). Note: a high abnormal or low abnormal laboratory value is not necessarily of clinical concern. The laboratory reference ranges will be provided on the listings of laboratory data. Clinical laboratory test results outside of the reference range will be flagged in the listings.

To identify laboratory values of potential clinical importance, National Cancer Institute Common Terminology Criteria for Adverse Events (NCI-CTCAE v4.0) will be used to assign grades to the relevant laboratory parameters. NCI-CTCAE v4.0 can be found at <http://ctep.cancer.gov/reporting/ctc.html>.

For laboratory data which are not listed in the NCI CTCAE v4.0, a summary of values outside the normal range will be provided.

16.8.2. ECG Parameters and vital signs

For ECG and vital signs, the most updated IDSL standard up to the RAP effective date will be followed

16.9. Appendix 9: Population Pharmacokinetic (PopPK) Analyses

16.9.1. Population Pharmacokinetic (PopPK) Dataset Specification

Any deviations between the dataset specification and the final dataset will be documented in the population pharmacokinetic analysis report.

General Description:

1. The type of variables should be either NUM or DATE/TIME unless specified otherwise
2. The dataset is sorted by ID, RTFDD, ANALYTE, ASCENDING EVID unless specified otherwise
3. The data items (columns) in the analysis-ready data file will be in the same order as described in the table below.
4. Exclude observations with DTYPE=IMPUTE
5. Include PKFL=Y (applicable to all datasets)
6. Same rules are applied for all baseline covariates. Baseline rules are as follows:
 - Use baseline value as defined by Stats in the lab test datasets and fill it on all rows for each subject;
 - If not defined by Stats, set to measurement nearest to, but prior to, time of first dose
 - Only in cases where Day 1 measurement is not available, but screening measurement is, the screening values will be used.
 - Only in cases where both the Day 1 measurement as well as screening measurement are unavailable, set to -99.
7. 3 significant figures for all values except C, STUDY, SUBJID, ID, CTIME, DATE, ANALN, BQL, MDV, MDV2, OCC, CYCLE, CMT, AGE, GENDER, CANCER, RACE, ETHN, CNC, EXTSMP
8. Only subjects with CANCER=0 will be included in this dataset as the data for the lymphoma patients will not be fully cleaned at the time of the database cut in 4Q2018.

CONFIDENTIAL

BMA117159

Column Header	Data Item	Codes	Derivation/Comments	Source data set
C	Line number/exclusion identifier	Row Number STM DRM PFD	Set to line/row number unless one or more of the following conditions are met, then set to code: 
 • STM = If a PK sample was taken but the date and/or time of the sample is missing and cannot be derived • DRM= PK samples for which dosing records are missing • PFD=PK samples with CONC reported as NA/NR/NQ/BQL/missing at pre-dose in CYCLE =1 	derived
STUDYID	Study ID		Unique identifier for a study	adpc
SITEID	Unique identifier for a study site			adsl
USUBJID	Unique subject identifier			adsl
SUBJID	Subject identifier from source data		SUBJID = SUBJID	adsl
ID	NONMEM subject identifier		Sequential subject identifier across studies after data is sorted by SUBJID. For study BMA117196, the ID will start with PPD For study 205678, the ID will start with PPD	derived
AMT	Amount of GSK2857916 given (in mg)		AMT = ALTDOSE, where PARAMCD=ALTDOSE only on the dosing line. If infusion was stopped early and then restarted, the dosing information will be captured with more than one line. Each line will represent a part of the infusion (for example from start to first interruption and then from restart to end of infusion). AMT will have to be derived separately from restart of infusion until it is stopped. For all other lines use "0"	adex
INFD	Infusion Duration (day)		INFD is the infusion duration and is computed from start and stop time of infusion (in days) (AENDTM-ASTDTM)/60/60/24 This value will only be used on the dosing line. For all other lines use "0" If infusion was stopped early and then restarted, INFD will have to be derived separately from restart of infusion until it is stopped.	adex
INFH	Infusion Duration (h)		INFH is the infusion duration and is computed from start and stop time of infusion (in h) (AENDTM-ASTDTM)/60/60 This value will only be used on the dosing line. For all other lines use "0" If infusion was stopped early and then restarted, INFH will have to be derived separately from restart of infusion until it is stopped.	adex

CONFIDENTIAL

BMA117159

Column Header	Data Item	Codes	Derivation/Comments	Source data set
RATED	Rate of infusion (mg/day)		RATED = AMT/INFD; This value will only be used on the dosing line. For all other lines use "0" If infusion was stopped early and then restarted, RATED will have to be derived separately from restart of infusion until it is stopped.	derived
RATEH	Rate of infusion (mg/h)		RATEH = AMT/INFH This value will only be used on the dosing line. For all other lines use "0" If infusion was stopped early and then restarted, RATEH will have to be derived separately from restart of infusion until it is stopped.	derived
RTFDD	Relative time from start of first infusion on study (day)		$RTFDD = ((ADTM - ASTDTM) / 60 / 60 / 24)$	adpc, adex
RTFDH	Relative time from start of first infusion on study (h)		$RTFDH = ((ADTM - ASTDTM) / 60 / 60)$	adpc, adex
RTLDD	Relative time from start of the most recent infusion on study (h) done prior to the PK sample		For pre-dose samples, RTLDD will be calculated considering the most recent infusion done prior to the sample. For example, the RTLDD for the pre-dose in Cycle 2 will be computed from the start time of infusion in Cycle 1.	adpc
RTLDD	Relative time from start of the most recent infusion on study (day) done prior to the PK sample		$RTLDD = RTLDDH / 24$	derived
NOMTLDD	Planned nominal time relative to start of most recent infusion (day)		$NOMTLDDH / 24$	adpc
NOMTLDDH	Planned nominal time relative to start of most recent infusion (h)		Derive from PCTPT when (PCTPT = 'PRE-DOSE'), NOMTLDDH = 0; when (PCTPT = 'DOSE'), NOMTLDDH = 0; when (PCTPT = "30M POST START OF INFUSION (SOI)"), NOMTLDDH = 0.5; when (PCTPT = "END OF INFUSION (EOI)"), NOMTLDDH = 1; when (PCTPT = "1 HOUR POST-EOI"), NOMTLDDH = 2; when (PCTPT = "3 HOURS POST-EOI"), NOMTLDDH = 4; when (PCTPT = "8 HOURS POST-EOI"), NOMTLDDH = 9; when (PCTPT = "24 HOURS POST-EOI"), NOMTLDDH = 25; when (PCTPT = "7 DAYS POST-EOI"), NOMTLDDH = 168; when (PCTPT = "14 DAYS POST-EOI"), NOMTLDDH = 336; when (PCTPT = "PRE-DOSE" and VISIT = CYCLE 2, NOMTLDDH = 504; when (PCTPT = "END OF STUDY"), NOMTLDDH = 10000;	adpc

CONFIDENTIAL

BMA117159

Column Header	Data Item	Codes	Derivation/Comments	Source data set
			otherwise NOMTLDH =.;	
CLOCK	Clock time sample was obtained	Clock time (24 h) '00:00'	TIMEPART (EVENT and DOSING LINE) Format TIME5.	all dataset
DATE	Date of event (MM/DD/YYYY)		DATEPART (EVENT and DOSING LINE) Format DATE9.	all dataset
ANALYTE	Analyte	1= ADC(antibody-drug conjugate) 2= TOTALMAB(total antibody including complex) 3= MMAF(cys-mcMMAF)	This value will be used on all lines except for dosing record line where missing "0" will be used. EXCLUDE MAB PARAMCD in (P1RES, P5RES, P7RES), assign ANALYTE =3, 1, 2 respectively	Derived from adpc
CONC	Plasma concentration (ng/mL) of GSK2857916 (antibody-drug conjugate), total antibody (including complex) and cys-mcMMAF		If AVALC=NA/NR/NQ/BQL/missing, set CONC= "0" Else CONC=AVAL When PARAMCD=P1RES, then CONC=AVAL/1000 [Convert cys-mcMMAF from pg/mL to ng/mL precision (3 significant figures). For example, 0.111 pg/mL= 0.000111 ng/mL]	adpc
DNCONC	Dose-normalized plasma concentration [(ng/mL)/(mg/kg)] of GSK2857916 (antibody-drug conjugate), total antibody (including complex) and cys-mcMMAF		DNCONC = CONC (ng/mL)/AVAL; where AVAL=adex.PARAMCD=ADOSE (mg/kg) For CONC = "0", set DNCONC = "0"	Derived from adpc, adex
CONCNM	Plasma concentration (nM) of GSK2857916 (antibody-drug conjugate), total antibody (including complex) and cys-mcMMAF		For ANALYTE = 1, CONCNM = CONC(ng/mL)/152.1 For ANALYTE = 2, CONCNM = CONC(ng/mL)/152.1 For ANALYTE = 3, CONCNM = CONC(ng/mL)/1.045 
 • MW of ANALYTE =1 is 152.1 kDa • MW of ANALYTE =2 is 152.1 kDa • MW of ANALYTE =3 is 1045 Da For CONC = "0", set CONCNM = "0"	Derived from adpc

CONFIDENTIAL

BMA117159

Column Header	Data Item	Codes	Derivation/Comments	Source data set
DNCONCNM	Dose-normalized plasma concentration [(nM)/(mg/kg)] of GSK2857916 (antibody-drug conjugate), total antibody (including complex) and cys-mcMMAF		DNCONCNM = CONCNM (nM)/ AVAL; where AVAL=adex.PARAMCD=ADOSE (mg/kg) For CONCNM = "0", set DNCONCNM = "0"	Derived from adpc
LNCONC	Natural logarithm of the plasma concentration of GSK2857916 (ng/mL) (antibody-drug conjugate), total antibody (including complex) and cys-mcMMAF		
 • If CONC = "0" then LNCONC = "0" • Else LNCONC = loge(CONC) 	Derived from adpc
LNDNCONC	Natural logarithm of dose-normalized plasma concentration [(ng/mL)/(mg/kg)] of GSK2857916 (antibody-drug conjugate), total antibody (including complex) and cys-mcMMAF		If DNCONC = "0" then LNDNCONC = "0" Else LNDNCONC = loge(DNCONC)	Derived from adpc
LNCONCNM	Natural logarithm of plasma concentration (nM) of GSK2857916 (antibody-drug conjugate), total antibody (including complex) and cys-mcMMAF		If CONCNM = "0" then LNCONCNM = "0" Else LNCONCNM = loge(CONCNM)	Derived from adpc
LNDNCONCNM	Natural logarithm of dose-normalized plasma concentration [(nM)/(mg/kg)] of GSK2857916 (antibody-drug conjugate), total antibody (including complex) and cys-mcMMAF		If DNCONCNM = "0" then LNDNCONCNM = "0" Else LNDNCONCNM = loge(DNCONCNM)	Derived from adpc
CONC2	Plasma concentration (ng/mL) of GSK2857916 (antibody-drug conjugate), total antibody (including complex) and cys-mcMMAF with imputation for BQL data		If adpc.AVALC=NA/NR/missing, set CONC2= "0" If AVALC=NQ/BQL, set CONC2 = "LLOQ/2" When PARAMCD=P1RES, then CONC2=AVAL/1000; [Convert cys-mcMMAF from pg/mL to ng/mL precision (3 significant figures). For example, 0.111 pg/mL= 0.000111 ng/mL] LLOQ for ANALYTE=1 is 100 ng/mL (adpc.PCLLOQ for PARAMCD=P5RES) LLOQ for ANALYTE=2 is 200 ng/mL (adpc.PCLLOQ for	Derived from adpc

CONFIDENTIAL

BMA117159

Column Header	Data Item	Codes	Derivation/Comments	Source data set
			PARAMCD=P7RES) LLOQ for ANALYTE=3 is 0.05 ng/mL (adpc.PCLLOQ for PARAMCD=P1RES; as it is in pg/mL, needs to be converted to ng/mL);	
DNCONC2	Dose-normalized plasma concentration[(ng/mL)/(mg/kg)] of GSK2857916 (antibody-drug conjugate), total antibody (including complex) and cys-mcMMAF with imputation for BQL data		DNCONC2 = CONC2(ng/mL)/ AVAL; where AVAL=adex.PARAMCD=ADOSE (mg/kg) For CONC2 = "0", set DNCONC2 = "0"	Derived from adpc, adex
CONCNM2	Plasma concentration (nM) of GSK2857916 (antibody-drug conjugate), total antibody (including complex) and cys-mcMMAF with imputation for BQL data		For ANALYTE = 1, CONCNM2 = CONC2(ng/mL)/152.1 For ANALYTE = 2, CONCNM2 = CONC2(ng/mL)/152.1 For ANALYTE = 3, CONCNM2 = CONC2(ng/mL)/1.045 For CONC2 = "0", set CONCNM2 = "0"	Derived from adpc
DNCONCNM2	Dose-normalized plasma concentration [(nM)/(mg/kg)] of GSK2857916 (antibody-drug conjugate), total antibody (including complex) and cys-mcMMAF with imputation for BQL data		DNCONCNM2 = CONCNM2 (nM)/ADOSE (mg/kg) For CONCNM2 = "0", set DNCONCNM2 = "0"	Derived from adpc
LNCONC2	Natural logarithm of the plasma concentration of GSK2857916 (ng/mL) (antibody-drug conjugate), total antibody (including complex) and cys-mcMMAF with imputation for BQL data		
 • If CONC2 = "0" then LNCONC2 = "0" • Else LNCONC2 = loge(CONC2) 	Derived from adpc
LNDNCONC2	Natural logarithm of dose-normalized plasma concentration [(ng/mL)/(mg/kg)] of GSK2857916 (antibody-drug conjugate), total antibody (including complex) and cys-mcMMAF with imputation for BQL data		If DNCONC2 = "0" then LNDNCONC2 = "0" Else LNDNCONC2 = loge(DNCONC2)	Derived from adpc
LNCONCNM2	Natural logarithm of plasma		If CONCNM2 = "0" then LNCONCNM2 = "0"	Derived from

CONFIDENTIAL

BMA117159

Column Header	Data Item	Codes	Derivation/Comments	Source data set
	concentration (nM) of GSK2857916 (antibody-drug conjugate), total antibody (including complex) and cys-mcMMAF with imputation for BQL data		Else LNCONCNM2 = loge(CONCNM2)	adpc
LNDNCONCNM2	Natural logarithm of dose-normalized plasma concentration [(nM)/(mg/kg)] of GSK2857916 (antibody-drug conjugate), total antibody (including complex) and cys-mcMMAF with imputation for BQL data		If DNCONCNM2 = "0" then LNDNCONCNM2 = "0" Else LNDNCONCNM2 = loge(DNCONCNM2)	Derived from adpc
BQL	Flag for BQL concentration	0 or 1	Set to 1 if adpc.AVALC= NQ/BQL; Else set to 0	adpc
MDV	Missing dependent variable flag.	0 or 1	1 for CONC = "0" and dosing line. 0 otherwise	adpc
MDV2	Missing dependent variable flag 2	0 or 1	1 for CONC2= "0" and dosing line. 0 otherwise	adpc
EVID	Flag indicating whether it is dosing admin info or drug concentration data.	0 or 1	1 on dosing line Set to 0 for all other lines	adex, adpc
CYCLE	Cycle number	>0	1 = Cycle 1, 2 = Cycle 2, 3 = Cycle 3, 4 = Cycle 4, 5 = Cycle 5,... etc EOT=999 Derive from AVISIT Fill CYCLE on all rows Note: Pre-dose belongs to the same cycle as the post dose sample done on the same day.	adpc
OCC	Occasion		If adpc.PCTPT=PRE-DOSE and CYCLE >= 2, then OCC= CYCLE-1, else OCC=CYCLE Fill OCC on all rows Note: This is different from CYCLE variable. OCC considers pre-dose sample to be part of prior cycle.	derived
EXTSMP	Subjects with extensive sampling/data	0= Subjects which do not have	1 will be assigned to subjects which have at least 4 CONC values above BLQ for either ANALYTE=1 or ANALYTE=3 up in OCC=1 0 for remaining subjects	adpc

CONFIDENTIAL

BMA117159

Column Header	Data Item	Codes	Derivation/Comments	Source data set
		extensive CONC for ADC/MM AF 1= Subjects with extensive CONC for ADC/MMAF	Fill EXTSMP on all rows	
IDOSE	GSK2857916 initial cycle dose (mg/kg)	>0	IDOSE=adex.TRT01A; strip off units	adex
ADOSE	GSK2857916 actual cycle dose (mg/kg)	>0	ADOSE= AVAL; where AVAL=adex. PARAMCD=ADOSE	adex
CMT	Compartment	>0	1 = Dosing line 1= Central Compartment for antibody-drug conjugate when ANALYTE=1 3 = Central Compartment for total antibody (including complex) when ANALYTE=2 5 = Central Compartment for cys-mcMMAF when ANALYTE=3	
RACET	Subject race text	Use CRF/Stats coding	RACET=adrace.ARACE Fill in RACET in all rows for each subject	adrace
RACEN	Subject race numeric		4 - ASIAN - JAPANESE HERITAGE 3 - ASIAN - SOUTH EAST ASIAN HERITAGE 2 - BLACK OR AFRICAN AMERICAN 1 - WHITE - ARABIC/NORTH AFRICAN HERITAGE 0 - WHITE - WHITE/CAUCASIAN/EUROPEAN HERITAGE	adrace
ETHN	Subject ethnicity	Same coding as CRF/Stats	Fill in ETHN in all rows for each subject - If missing, ETHN = -99	adsl
AGE	Age (years)		• Use value as defined by Stats; • If not defined by Stats, AGE = date of first dose – date of birth • If date of birth is missing, AGE = -99	adsl
SEX	Gender	0 or 1	Male = 1 Female = 0	adsl

CONFIDENTIAL

BMA117159

Column Header	Data Item	Codes	Derivation/Comments	Source data set
			
 If sex is missing, SEX = -99 	
BWT	Baseline Weight (kg)		Use Baseline covariate rules. Fill in BWT in all rows for each subject	adsl
WT	Weight (kg)		WT is propagated forward from the most recent measurement for all observations up to the next WT measurement (LOCF). Please capture the values corresponding to the PK time points.	advs
HT	Height (cm)		Height at baseline in cm Fill in HT in all rows for each subject	adsl
BBSA	Baseline Body Surface Area (m ²)		Baseline BSA (m ²) $BSA = 0.024265 \cdot HT(cm)^{0.3964} \cdot BWT(kg)^{0.5378}$ Ref: Geometric method for measuring body surface area: a height-weight formula validated in infants, children, and adults. Haycock GB, Schwartz GJ, Wisotsky DH. Use baseline covariate rules	derived
BSA	Body Surface Area (m ²)		BSA (m ²) $BSA = 0.024265 \cdot HT(cm)^{0.3964} \cdot WT(kg)^{0.5378}$ BSA is propagated forward from the most recent measurement for all observations up to the next BSA measurement (LOCF). Please capture the values corresponding to the PK time points.	derived
BBMI	Baseline Body Mass Index (kg/m ²)		$BBMI = BWT(kg)/(HT(cm)/100)^2$ Assign BBMI = -99 if negative values would be derived for any of BBMI Use baseline covariate rules	derived
BMI	Body Mass Index (kg/m ²)		$BMI = WT(kg)/(HT(cm)/100)^2$ Assign BMI = -99 if negative values would be derived for any of BMI BMI is propagated forward from the most recent measurement for all observations up to the next BMI measurement (LOCF). Please capture the values corresponding to the PK time points.	derived
CANCER	Cancer type	0 or 1	0=Multiple Myeloma, 1=BCMA positive Lymphomas If TRT01AN = 12, then CANCER=1, else CANCER=0 Fill in CANCER in all rows for each subject	all datasets
BSBCMA	sBCMA level at baseline (ng/mL)		Baseline value is pre-dose on Cycle 1 Day 1. For PARAMCD = SBCMAG, get the values from AVAL column. When AVAL is missing: 
 and AVALC = ALQ: set to LBULOQ and AVALC = BLQ: set to LBLLOQ/2 	adbiomrk PARAMCD = SBCMAG when ABLFL=Y.

CONFIDENTIAL

BMA117159

Column Header	Data Item	Codes	Derivation/Comments	Source data set
			
 and AVALC = missing: set to -99 Use baseline covariate rules	
SBCMA	sBCMA level (ng/mL)		For PARAMCD = SBCMAG, get the values from AVAL column. SBCMA is propagated forward from the most recent measurement for all observations up to the next sBCMA measurement (LOCF). When AVAL is missing: 
 and AVALC = ALQ: set to LBULOQ and AVALC = BLQ: set to LBLLOQ/2 and AVALC = missing: propagate prior SBCMA value forward until the next measured SBCMA Please capture the values corresponding to the PK time points.	adbiomrk PARAMCD = SBCMA
SBCMAGC	Complex BCMA (ng/mL)		For PARAMCD = SBCMAGC, get the values from AVAL column. SBCMAGC is propagated forward from the most recent measurement for all observations up to the SBCMAGC measurement (LOCF). When AVAL is missing: 
 and AVALC = ALQ: set to LBULOQ and AVALC = BLQ: set to LBLLOQ/2 and AVALC = missing: propagate prior SBCMAGC value forward until the next measured SBCMAGC Please capture the values corresponding to the PK time points.	adbiomrk PARAMCD = SBCMAGC
BCRCL	Baseline Creatinine Clearance (mL/min/1.73 m ²)		$eGFR = 175 \times (Scr)^{-1.154} \times (Age)^{-0.203} \times (0.742 \text{ if female}) \times (1.212 \text{ if African American})$ Scr = AVAL; AVAL=adlab.PARAMCD =LB1404 and ABLFL=Y Convert units (μmol/L) to (mg/dL) using the following formula: To convert μmol/L to mg/dL, multiply by 0.0113. Age is expressed in years. Use baseline covariate rules Ref: Protocol	adlb; PARAMCD=L B1404

CONFIDENTIAL

BMA117159

Column Header	Data Item	Codes	Derivation/Comments	Source data set		
			
16.4. Appendix 5: Modified Diet in Renal Disease Formula
 
 
 MDRD	 $eGFR = 175 \times (SCr)^{-1.154} \times (Age)^{-0.203} \times (0.742 \text{ if female}) \times (1.212 \text{ if African American})$ 	
 
 
GFR is expressed in mL/min/1.73 m², SCr is serum creatinine expressed in mg/dL, and age is expressed in years.
 
The link below will auto-calculate the creatinine clearance:
 
http://nephron.org/cgi-bin/MDRD_GFR/cgi
	MDRD	$eGFR = 175 \times (SCr)^{-1.154} \times (Age)^{-0.203} \times (0.742 \text{ if female}) \times (1.212 \text{ if African American})$	
MDRD	$eGFR = 175 \times (SCr)^{-1.154} \times (Age)^{-0.203} \times (0.742 \text{ if female}) \times (1.212 \text{ if African American})$					
CRCL	Creatinine Clearance (mL/min/1.73 m ²)		
To be computed with same equation as provided for BCRCL
 
CRCL is propagated forward from the most recent measurement for all observations up to the next CRCL measurement (LOCF). Please capture the values corresponding to the PK time points.
	adlb		
BALT	Baseline ALT (IU/L)		
BALT = AVAL; AVAL=adlab. PARAMCD =LB1227 and ABLFL=Y Use baseline covariate rules
	adlb		
ALT	ALT (IU/L)		
ALT = AVAL; AVAL=adlab. PARAMCD =LB1227 and ABLFL=Y ALT is propagated forward from the most recent measurement for all observations up to the next ALT measurement (LOCF). Please capture the values corresponding to the PK time points.
	adlb		
BAST	Baseline AST (IU/L)		
BAST = AVAL; AVAL=adlab. PARAMCD =LB1273 and ABLFL=Y Use baseline covariate rules
	adlb		
AST	AST (IU/L)		
AST = AVAL; AVAL=adlab. PARAMCD =LB1273 and ABLFL=Y AST is propagated forward from the most recent measurement for all observations up to the next AST measurement (LOCF). Please capture the values corresponding to the PK time points.
	adlb		
BALB	Baseline Albumin (g/L)		
BALB = AVAL; AVAL=adlab. PARAMCD =LB1216 and ABLFL=Y Use baseline covariate rules
	adlb		
ALB	Albumin (g/L)		
ALB = AVAL; AVAL=adlab. PARAMCD =LB1216 and ABLFL=Y ALB is propagated forward from the most recent measurement for all observations up to the next ALB measurement (LOCF). Please capture the values corresponding to the PK time points.
	adlb		
BTBIL	Baseline Total Bilirubin (mg/dL)		
BTBIL = AVAL; AVAL=adlab. PARAMCD =LB1282 and ABLFL=Y
	adlb		

CONFIDENTIAL

BMA117159

Column Header	Data Item	Codes	Derivation/Comments	Source data set
			Use baseline covariate rules	
TBIL	Total Bilirubin (mg/dL)		TBIL = AVAL; AVAL=adlab. PARAMCD =LB1282 and ABLFL=Y TBIL is propagated forward from the most recent measurement for all observations up to the next TBIL measurement (LOCF). Please capture the values corresponding to the PK time points.	adlb
BCRP	Baseline C Reactive Protein (mg/L)		Use baseline covariate rules	adlb
CRP	C Reactive Protein (mg/L)		CRP is propagated forward from the most recent measurement for all observations up to the next CRP measurement (LOCF). Please capture the values corresponding to the PK time points.	
BIGG	Baseline serum IgG (g/L)		BIGG = AVAL; AVAL=adlab. PARAMCD =LB1566 and ABLFL=Y Use baseline covariate rules	adlb
IGG	Serum IgG (g/L)		IGG = AVAL; AVAL=adlab PARAMCD =LB1566 Missing values use -99. IGG is propagated forward from the most recent measurement for all observations up to the next IGG measurement (LOCF). Please capture the values corresponding to the PK time points.	adlb
MAXPRED	Maximum reduction in M-protein or FLC		Obtain AVAL for PARAMCD=MAXPRED. When AVAL is missing, MAXPRED = -999	adrs
RESPRATIO	Transform MAXRED to a ratio to baseline		RESPRATIO = $\max((100+\text{MAXPRED})/100, 0.001)$ 
 • When MAXRED is missing, MAXPRED = -999 and RESPRATIO= -99 • When MAXPRED is less than -100 e.g. -100.15, RESPRATIO = negative (It is negative but greater than -8.99), then update RESPRATIO = 0.001 • When MAXPRED is equal to -100, RESPRATIO = 0, then update RESPRATIO = 0.001 	adrs
COUNTRY	Country code		Fill in COUNTRY in all rows for each subject	adsl
CNC	NONMEM Country code	1 = Canada, 2 = UK	Fill in CNC in all rows for each subject	adsl

CONFIDENTIAL

BMA117159

Column Header	Data Item	Codes	Derivation/Comments	Source data set																												
		3 = US																														
IMMU	Immunogenicity Outcome by Collection Time	0 = negative 1 = positive	
  
 	PARAMCD	IMMU	
 
 	PARAMCD = AGBABDS	PARAMCD = AGBABDC		
   
 AVAL C	NEGATIVE	MISSING	0	
 
 AVAL C	POSITIVE	POSITIVE	1	
 
 AVAL C	POSITIVE	NEGATIVE	0	
 
 AVAL C	POSITIVE	MISSING	-99	
 
 AVAL C	MISSING	ANY	-99	
  
 
IMMU may not have been assayed at all PK visits. For visits between IMMU visits, imputation rules are as follows:
 
(1) When there is no change in IMMU between IMMU visits, all PK visits in between will be imputed with
		PARAMCD		IMMU		PARAMCD = AGBABDS	PARAMCD = AGBABDC		AVAL C	NEGATIVE	MISSING	0	AVAL C	POSITIVE	POSITIVE	1	AVAL C	POSITIVE	NEGATIVE	0	AVAL C	POSITIVE	MISSING	-99	AVAL C	MISSING	ANY	-99	adis
	PARAMCD		IMMU																													
	PARAMCD = AGBABDS	PARAMCD = AGBABDC																														
AVAL C	NEGATIVE	MISSING	0																													
AVAL C	POSITIVE	POSITIVE	1																													
AVAL C	POSITIVE	NEGATIVE	0																													
